## 9 ADVERSE EVENT REPORTING

#### 9.1 Adverse Events

An Adverse Event is any untoward medical occurrence in a Subject, regardless if there is a relationship between the adverse event(s) and the study device(s).

At each evaluation of the Subject enrolled in a clinical investigation, the Investigator determines whether any adverse events (AE) have occurred and determines their relationship to the study devices or procedure. For the purposes of this study, only serious adverse events (see Section 9.2), device and/or procedure related adverse events will be reported to the Sponsor.

All non-serious reportable adverse events, study device malfunctions and other product issues must be recorded in the medical records and entered into electronic Case Report Forms (eCRFs) as soon as possible but no later than two weeks after awareness of the AE having occurred. Upon entry of an AE into the eCRF, designated members of the DePuy Synthes clinical team will receive an email alert describing the AE.

#### 9.2 Serious Adverse Events

Serious Adverse Events (SAEs) are defined as any adverse event that:

1. Led to a death,

- 2. Led to a serious deterioration in the health of the Subject that,
- a. Resulted in life-threatening illness or injury,
- b. Resulted in permanent impairment of a body structure or a body function,
- c. Required in-patient hospitalization or prolongation of existing hospitalization
- d. Resulted in medical or surgical intervention to prevent life threatening illness or injury or permanent impairment to a body structure or a body function,
- 3. Led to fetal distress, fetal death or a congenital abnormality or birth defect
- 4. Led to chronic disease

A planned hospitalization and/or medical intervention for pre-existing conditions documented in the study records that have not changed in severity, or a procedure required by the protocol, without serious deterioration in health, is not considered to be a serious adverse event.

Investigator must submit to DePuy Synthes any SAEs occurring during the study as soon as possible, but within 72 hours, after becoming aware of the event and provide additional information if required by DePuy Synthes. All SAEs need to be followed until the event is resolved (with or without sequelae), additional information is located in Section 9.3. The Study Safety Lead of this study will decide if more follow-up information is needed (via electronic queries) in case the event is not resolved at study completion.

The Investigator notifies his/her REB of all SAEs as required by REB policy (and any additional information as required by REB).

#### 9.3 Duration of Follow-up After Adverse Events

4 MAR 2022; Version Rev 3 DSJ-2019-02 Confidential

Page **24** of **47** TV-eFRM-02920 The Investigator should ensure that adequate medical care is provided to any Subject for any adverse events related to the study.

Only SAEs, device and/or procedure related Adverse Events will be collected for the purposes of this study. All device or procedure adverse events should be followed until the condition has resolved, or in the case of permanent impairment until the condition stabilizes and clinical outcome has been ascertained, or the study has been completed.

## 9.4 Reporting an Adverse Event

Adverse events are reported from the time of surgery until the Subject's study participation has ended (i.e. completion of study or withdrawal of consent). All reported AEs must be followed until the AE has resolved, stabilized, or the study has been completed. Any medical event, that if it had occurred post-operatively would be considered a serious adverse event, that occurs prior to surgery is to be reported as history on the Medical History eCRF.

The Investigator will record the nature, severity, treatment and outcome of the AE, and will determine its relationship to the investigational products or any protocol mandated procedures involved in the clinical study.

The determination whether the AE is related to the device and/or procedure will be based upon whether a causal relationship between the device and/or procedure and the AE is at least a reasonable possibility, i.e. the relationship cannot be ruled out. A causal relationship cannot be ruled out if, in the medical judgment of the Investigator, the effect follows a reasonable temporal association with the use of the device and/or is confirmed by the improvement of the effect upon discontinuation of the clinical use of the device, and/or the effect is not reasonably explained by the Subject's clinical state.

Relationship to study device or procedure should be rated as follows:

1) Not related (definitely not related): there is no relationship between study device and/or procedure and the event.

2) Possibly related (remote possibility, possibly, or probably related): the relationship between study device and/or procedure could exist if there is no contradicting evidence that can reasonably explain the Subject's condition.

3) Definitely related (definitely related): the relationship between study device and/or procedure and event does exist and is confirmed upon further investigation by the Investigator.

	ine following categories of adverse event severity are to be used.				
MildAwareness of sign or symptom that does not inter Subject's usual activity or is transient, resolved w treatment and with no sequelae,		Awareness of sign or symptom that does not interfere with the Subject's usual activity or is transient, resolved without treatment and with no sequelae,			
	Moderate	Interferes, but does not hinder, the Subject's usual activity and may require treatment,			
	Severe	Symptom(s) causing severe discomfort and significant impact on the Subject's usual activity and requires treatment or intervention.			

#### The following categories of adverse event severity are to be used:

For all serious and device/procedure-related adverse events, the Investigator is responsible for determining whether the adverse events are anticipated or unanticipated. This determination is based on whether the severity, type and frequency of the adverse event is consistent with the Instructions for Use (IFU) in the opinion of the Investigator.

Adverse events will be reported by the Investigator to DePuy Synthes via the Adverse Events eCRF.

NOTE: Please refer to Appendix B (Anticipated Adverse Events) where a listing of common surgical adverse events is listed. These adverse events are anticipated and assuming the events are consistent with the normal postoperative course, then they do not have to be reported as adverse events.

## **10 EARLY DISCONTINUATION**

#### 10.1 Reasons for Early Discontinuation

Possible reasons for early discontinuation may include, but are not limited to the following:

- Withdrawal of consent: Subject decides to withdraw from the study. This decision must be an "independent decision" that is documented in the patient study files;
- Adverse event: Adverse event or serious adverse event may not lead to Subject discontinuation from the study. If the Investigator decides to discontinue further study related procedures, the Subject must still be followed until the adverse event resolves or until a stable clinical endpoint is reached, or the Subject withdraws consent (i.e., the Subject will continue to be followed for safety);
- Revision of any component;
- Death, and/or
- Early study termination: DePuy Synthes can decide to discontinue the study prematurely for various reasons.

#### 10.2 Subject Early Discontinuation

Every Subject should be encouraged to remain in the study until they have completed the protocolrequired 2-year follow-up period. If the Subject discontinues prematurely from the study, the reason for discontinuation must be documented in the source documents and site files and submitted via eCRF.

Data which have been received on Subjects who discontinue prematurely will be included in the analysis of results. Subjects who discontinue prematurely, excluding those withdrawn preoperatively, intra-operatively or those Subjects who were unable to complete their 6 week visit due to the COVID-19 Pandemic, will not be replaced.

#### 10.3 Study Early Discontinuation

DePuy Synthes reserves the right to temporarily suspend or prematurely discontinue this study either at a single site, multiple sites, or at all sites at any time for reasons including, but not limited

Page 26 of 47

to, safety or ethical issues, inaccurate or incomplete data recording, non-compliance, or unsatisfactory enrollment with respect to quality or quantity.

If the study is prematurely terminated or suspended, DePuy Synthes or its representatives will inform the Investigators/institutions of the termination or suspension and the reason(s) for the termination or suspension, in accordance with applicable regulatory requirement(s). The REB should also be informed and provided with reason(s) for the termination or suspension by DePuy Synthes or by the Investigator/institution, as specified by the applicable regulatory requirement(s). In addition, arrangements will be made for the return of all study material in accordance with Sponsor procedure for the study.

## **11 STATISTICAL METHODOLOGY**

The following sections provide a general description of the statistical plan for the analysis of study data. A separate Statistical Analysis Plan (SAP) document that provides greater detail on data derivations and the analyses to be performed will be finalized prior to database lock. The SAP will reflect the protocol and any amendments that have been implemented at the time the SAP is finalized. Any deviations from the final SAP will be noted in the final clinical summary report.

#### 11.1 Study Design

This is a prospective, multi-center, non-randomized, non-controlled study designed to establish the 2-year migration profile of the PINNACLE® DM Construct.

#### **11.2 Treatment Assignment**

Subjects enrolled will undergo THA using the study devices listed in Section 5.5.

#### 11.3 Randomization and Blinding Procedures

Not applicable.

#### 11.4 Interval Windows

Data collected throughout the study will be assessed for compliance with the protocol-specified visit schedule. Six windows are defined based on the number of days prior to or after surgery, Day 0. Visits conducted within the intervals shown in Table 11-1 will be assessed for compliance with the protocol. If multiple visits fall into the pre-operative window, or into the 6 Week post-operative window, the result collected most proximate to surgery will be utilized. If multiple measurements fall into the 3 Month, 6 Month, 1 Year, or 2 Year window, the last value (furthest from surgery) will be utilized for the analysis. All safety data will be included in the Safety analysis.

Study Visit	Study Interval Window (days)	
Pre-Op	-90 to DOS*	
Operative	0	
Prior to Discharge	Day 1 to Discharge	
6 Weeks	28 to 56	

Table 11-1 Study Visit Interval Windows per Time and Events Table

4 MAR 2022; Version Rev 3 DSJ-2019-02 Confidential Page 27 of 47

3 Months	60 to 120
6 Months	135 to 225
1 Year	275 to 455
2 Years	640 to 820

\* For radiographs Pre-Op study film window is from -270 days to date of surgery (DOS).

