#### 8.6 Unscheduled Visit

An unscheduled visit is to be documented on an Unscheduled Visit eCRF/CRF when:

1. A Subject returns for an additional visit during a study visit interval as described in Table 3.2

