#### - Time and Events.

2. A Subject returns between study visit intervals

If a Subject requires an additional visit during a study interval, and is seen by one or more persons listed on the Delegation of Authority Log, then the following information shall be repeated:

- Harris Hip Score
- Hip Evaluation
- HOOS Jr.
- Forgotten Joint Score
- Adverse Events (if applicable)

If a Subject has an unscheduled visit after the 6 week interval (outside defined protocol window), with one or more persons listed on the Delegation of Authority Log then the following information shall be collected:

- Harris Hip Score
- Hip Evaluation
- HOOS Jr.
- Forgotten Joint Score

4 MAR 2022; Version Rev 3 DSJ-2019-02 Confidential Page **22** of **47** TV-eFRM-02920

- Adverse Events (if applicable)
- Radiographs
  - o AP Femur
  - o Lateral
- RSA Exam (supine position) if RSA Exam was not conducted in-window for previous visit. If Subject is seen multiple times outside of the same defined protocol window, only one RSA Exam is required.

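### In four visit windows the last-value rule lets a later unscheduled visit replace the scheduled Harris Hip Score, HOOS Jr. and FJS-12, which could bias these secondary results

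*Combined protocol and SAP*

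**What the plan says.** Section 11.4 sets the rule for repeated measurements in the 3-month, 6-month, 1-year and 2-year windows: "the last value (furthest from surgery) will be utilized for the analysis". The Pre-Op and 6 Week windows go the other way; for the latter the text reads "or into the 6 Week post-operative window, the result collected most proximate to surgery will be utilized". Neither rule distinguishes scheduled from unscheduled visits.

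Section 8.6 counts as unscheduled any occasion when "A Subject returns for an additional visit during a study visit interval", separately from returns between intervals. For the in-window case it says "If a Subject requires an additional visit during a study interval" and the subject is seen by someone on the delegation log, "then the following information shall be repeated". The list that follows holds the Harris Hip Score, hip evaluation, HOOS Jr., Forgotten Joint Score and adverse events. RSA is not on it. RSA appears only in the list for visits outside a window, and then only "if RSA Exam was not conducted in-window for previous visit".

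Section 11.12.2 summarizes each of the three scores from whatever results lie in the visit window. Section 11.12.4 compares them with DSJ_2018_02 by t-test, confidence interval and p-value. Section 11.12.3 allows an exploratory correlation of the scores with RSA.

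**The concern.** Each rule is unremarkable alone. Together they make a second in-window score compulsory for some subjects and then prefer it to the planned one. Which subjects have a second score depends on who needed another visit, and that may well be related to how the hip is doing. The value analysed at a nominal visit could then be selected partly by outcome.

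Three uses of the scores are affected: the visit means and changes from baseline, the comparison with the historical construct, and the exploratory correlation with RSA. For the correlation there is a further problem. The replaced score carries the date of the extra visit while the RSA value keeps the date of the scheduled one.

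**Working it through.** **The plan's own precision figure.** Section 11.8 gives a margin of 2 × 0.2/√30 = 0.073 mm for mean 2-year subsidence. It reproduces. It is not affected here, because in-window extra visits add no RSA measurement.

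**Room for an overwrite.** Window limits come from Table 11-1. Midpoints are (60+120)/2 = 90, (135+225)/2 = 180, (275+455)/2 = 365 and (640+820)/2 = 730. Assume the scheduled visit falls at the midpoint.

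| Window | Days | Length (days) | Days left after midpoint |
|---|---|---|---|
| 3 months | 60–120 | 61 | 30 |
| 6 months | 135–225 | 91 | 45 |
| 1 year | 275–455 | 181 | 90 |
| 2 years | 640–820 | 181 | 90 |

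At 1 and 2 years a replaced score could therefore be dated up to about 90 days after the RSA exam paired with it.

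**Shift in a visit mean.** If m of n subjects have a later in-window score that differs by d points from the scheduled one, the mean moves by (m/n) × d. The documents give neither m nor d, so both are assumed. At n = 30, the planned minimum:

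| m | d = 5 | d = 10 | d = 20 |
|---|---|---|---|
| 1 | 0.17 | 0.33 | 0.67 |
| 3 | 0.50 | 1.00 | 2.00 |

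At n = 45, the planned maximum, the same cases give 0.11 to 0.44 points (m = 1) and 0.33 to 1.33 points (m = 3).

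**Against the sampling error.** The protocol states no SD for the scores. Assuming 15 points, the standard error at n = 30 is 15/√30 = 2.74. For a shift of b standard errors, approximate coverage of the 95% interval is Φ(1.96 − b) − Φ(−1.96 − b).

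- m = 1, d = 5: b = 0.17/2.74 = 0.06; coverage 95.0%.
- m = 3, d = 10: b = 1.00/2.74 = 0.37; coverage 93.5%.
- m = 3, d = 20: b = 2.00/2.74 = 0.73; coverage 88.7%.

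**The case against.** The strongest reply is that no bias has been shown. Section 8.6 does not say why a subject returns, how often this happens, or that the reason is a complaint. Recovery within a window of 61 to 181 days could raise later scores rather than lower them. The last-value rule is pre-specified and deterministic. The endpoints are secondary, without hypotheses, and the historical comparisons are offered only as an aid to clinical judgement. Unscheduled visits have their own form, so scheduled scores stay recoverable, and data derivations are left to a separate SAP. If extra visits are symptom-driven, ignoring them would also move results in the favourable direction.

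Most of this limits the size of the point but does not remove it. Direction and size are indeed unknown. But this is a stated rule, not a detail left open: Section 11 says the SAP will follow the protocol, so the rule carries forward unless changed. An estimate meant to inform judgement should still describe the visit it is labelled with. The remark about favourable direction is a fair reason to report both versions.

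A reader might go further and infer that about a third of extra visits would overwrite a score, since (30+45+90+90)/761 = 255/761 = 34% of days 60 to 820 lie in the later halves of the windows. That assumes extra visits are spread evenly over time, which sits badly with the idea that problems prompt them. It is also a share of visits pooled over four windows, not of subjects at one visit. On that same assumption the later half of a 1- or 2-year window holds 90/761 = 11.8% of the days, so overwriting 20% of subjects there would take about 0.20/0.118 = 1.7 extra visits per subject. At 3 months (30/761 = 3.9%) it would take about 5. A 4-point shift (6 of 30 subjects, 20 points each) therefore has no support in the documents.

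**Conclusion.** The overwrite follows directly from Sections 8.6 and 11.4 and reaches all three scores at 3 months, 6 months, 1 year and 2 years. Bias is a plausible risk, not an established result. It needs extra visits that fall after the scheduled one in the same window and whose scores differ systematically from it. Under the assumed inputs the effect runs from negligible (one subject, 5 points) to about 0.7 of a standard error (three subjects, 20 points, SD 15).

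Two wider readings do not hold. The rule does not favour the latest value in every window, since Pre-Op and 6 Week take the value nearest surgery. The primary endpoint is not at risk by this route. The change is still worth making: it removes a possibly outcome-related selection from secondary endpoints that are tested against historical data, and it needs no new data.

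**What to change.** In Section 11.4 and in the SAP, before database lock:

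- For the three functional scores in the 3-month, 6-month, 1-year and 2-year windows, use the score from the scheduled visit.
- Use an unscheduled in-window score only when no scheduled score exists. If several qualify, take the one closest to the window midpoint (day 90, 180, 365 or 730). These days are derived from Table 11-1 and should be written in as the target days.
- Apply the same rule to the DSJ_2018_02 scores where possible, and state which rule those data follow. The documents do not say.
- Report the last-value rule as a sensitivity analysis.

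The cost is a short change of text and a small amount of extra analysis. The one real downside is a possible mismatch with DSJ_2018_02 if its scores cannot be re-derived under the same rule. In that case the report should say so and show the comparison both ways.

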#### 11.5 Analysis Sets

#### Safety Analysis Set

The Safety Analysis Set consists of all enrolled Subjects who receive THA surgery. Subjects will be analyzed according to the surgical approach applied during of the study.

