#### 6.3 Definition of Subject Enrollment

A patient will be considered enrolled when they have provided signed Informed Consent Document (ICD) to participate in this Investigation, which includes authorization of the release of his/her Protected Health Information (PHI).

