#### 8.2 Operative (Day 0)

Each Subject will receive a DePuy femoral stem with a polished neck in combination with a DePuy PINNACLE® acetabular cup. All Subjects will receive a PINNACLE® DM metal liner and a BI-MENTUMTM ALTRX® Dual Mobility Polyethylene Liner. Either metal or ceramic heads may be used; however, compatibilities must align with product labeling. Please note since revisions of existing THAs are acceptable to enroll into this study, variations in what is implanted will occur, however Subjects must receive the PINNACLE® DM metal liner and a BI-MENTUMTM ALTRX® Dual Mobility Polyethylene Liner. If the surgeon determines intraoperatively that there exists insufficient bone quality to support the implantation of the construct that Subject will be withdrawn from the study. Subjects that are withdrawn pre-operatively or intra-operatively will be replaced in order to have a minimum of 30 and up to 45 Subjects implanted with the study devices.

Each surgeon shall perform the surgical approach they are most comfortable with and have the greatest expertise.

Implant sizing shall be performed as per the surgeon's discretion for each individual Subject and will not be standardized between sites. Approximately 5-10 tantalum beads will be placed into the

4 MAR 2022; Version Rev 3 DSJ-2019-02 Confidential Page **20** of **47** TV-eFRM-02920 acetabulum. Bead placement will be standardized across study sites to reduce the possibility of unuseable RSA exams resulting from poor bead spacing or bead occlusion.

Any intra-operative adverse events will be captured as well as details of the surgery and implants/components used. The information collected from the 'Operative' time-point will be populated on the appropriate eCRFs as indicated in the Time and Events Table (Section 3.2).

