#### 11.13 Safety Endpoint Analysis

Adverse Events will be coded according to the Medical Dictionary for Regulatory Activities (MedDRA) version 21.1. Analyses will be conducted for all Subjects in the Safety Analysis Set.

An overall summary of the AE incidence will be presented and will include the number and percentage of Subjects having one or more:

- Serious adverse event (SAE)
- Device related AEs
- Procedure related AEs
- Withdrawals due to AE
- Deaths

The number (%) of Subjects with adverse events will be presented by MedDRA system organ class (SOC) and preferred term (PT) for all device related AEs, procedure related AEs and SAEs. A Subject-level listing will be provided to display details of all reported AEs.

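### The Safety Analysis Set does not require that the study construct was implanted, so device-related event percentages can include Subjects who never carried it, and intraprosthetic dislocation has no stated denominator

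*Combined protocol and SAP*

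**What the plan says.** Enrolment happens at consent, before any implant. Section 6.3: "A patient will be considered enrolled when they have provided signed Informed Consent Document (ICD) to participate in this Investigation".

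The safety population in section 11.5 has two conditions only, enrolment and THA surgery: "The Safety Analysis Set consists of all enrolled Subjects who receive THA surgery". The same section classifies these Subjects by surgical approach, not by the device received.

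Section 8.2 provides for leaving the trial when the construct cannot be used: "If the surgeon determines intraoperatively that there exists insufficient bone quality to support the implantation of the construct that Subject will be withdrawn from the" […]. On replacement, it says: "Subjects that are withdrawn pre-operatively or intra-operatively will be replaced in order to have a minimum of 30 and up to 45 Subjects implanted"; the implants meant are those of this trial. Section 10.2 keeps the data already received on Subjects who discontinue early.

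Section 11.13 sets the safety denominator: "Analyses will be conducted for all Subjects in the Safety Analysis Set". The statistic is a simple proportion: "An overall summary of the AE incidence will be presented and will include the number and percentage of Subjects having one or more" of five event types. Device-related events are one of the five. No adjustment for exposure time is planned.

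Section 11.12.3 plans a summary of the incidence of intraprosthetic dislocation but names no analysis set for it.

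**The concern.** Section 8.2 identifies the exposed population, those implanted with the study devices, but section 11.5 never makes it an analysis set. A Subject withdrawn at surgery who leaves with another THA construct meets both conditions of the Safety Analysis Set. That Subject then counts in the denominator of a percentage that will be read as the device-related event rate of the dual mobility construct. Unless such Subjects have device-related events of their own, each one lowers that percentage.

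Intraprosthetic dislocation has a related gap. It can occur only in a Subject who has the dual mobility liner, yet the denominator is left open. If the Safety Analysis Set were used by default, the same dilution would follow.

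What is at stake is how accurately the construct's device-related rate is described in a study of 30 to 45 implanted Subjects, where one or two people move a percentage visibly. No test or safety threshold depends on it.

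**Working it through.** **The plan's own figure.** The documents give no expected safety rate and no precision target for one. The only sample-size figure is the margin of error in section 11.8: 2 × 0.2/√30 = 0.073 mm. It reproduces, and this point does not depend on it.

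**Who is in the set.**
1. A consented Subject is enrolled (6.3).
2. If the bone cannot support the construct, the Subject is withdrawn during surgery (8.2).
3. If that Subject still receives a THA with other components, both conditions of 11.5 are met. A Subject who leaves without any THA does not meet them and does not count in k.
4. No section removes the Subject in step 3. Section 11.2 says enrolled Subjects will have THA with the study devices, but that is the planned treatment, and 8.2 provides for its not happening.
5. Replacement under 8.2 means these Subjects come on top of the 30 to 45 implanted.

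**Inputs.** N = Subjects implanted with the construct, 30 to 45 (8.2). k = Subjects in step 3; the documents give no value, so 0 to 5 is assumed. x = implanted Subjects with a device-related event; x = 3 is used for illustration. None of the k Subjects is assumed to have a device-related event.

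**Formula.** Rate among the implanted: x/N. Rate under 11.13: x/(N+k). Relative reduction: 1 − [x/(N+k)]/[x/N] = k/(N+k), whatever the value of x.

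| N | k | k/(N+k) | x = 3 under 11.13 | x = 3 among implanted |
|---|---|---|---|---|
| 30 | 0 | 0% | 3/30 = 10.0% | 10.0% |
| 30 | 1 | 1/31 = 3.2% | 3/31 = 9.7% | 10.0% |
| 30 | 3 | 3/33 = 9.1% | 3/33 = 9.1% | 10.0% |
| 30 | 5 | 5/35 = 14.3% | 3/35 = 8.6% | 10.0% |
| 45 | 1 | 1/46 = 2.2% | 3/46 = 6.5% | 6.7% |
| 45 | 3 | 3/48 = 6.25% | 3/48 = 6.25% | 6.7% |
| 45 | 5 | 5/50 = 10.0% | 3/50 = 6.0% | 6.7% |

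**By surgical approach.** Section 11.9 reports endpoints by approach as well as overall. In an assumed stratum of 10 implanted Subjects, one added Subject lowers the stratum's rate by 1/11 = 9.1%.

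**Intraprosthetic dislocation.** The synopsis promises 95% confidence intervals for exploratory outcomes, which include this one. With no event, the exact two-sided upper limit is 1 − 0.025^(1/n): 11.6% for n = 30, 11.2% for n = 31, 10.6% for n = 33 and 10.0% for n = 35. The difference arises only if the Safety Analysis Set is taken as the denominator, which the text neither says nor excludes.

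**Primary endpoint.** Section 11.12.1 uses Subjects with both 6-week and 2-year data, in the Per Protocol set and in the supportive Safety Set analysis. A Subject withdrawn at surgery has neither and drops out of both.

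**The case against.** The strongest reply is that this may never happen. Exclusion criteria 3 and 5 in section 6.2 screen out inadequate bone and unsuitable candidates before surgery, so k may well be 0, and then nothing changes. Three to five withdrawals per 30 implanted would mean that 9% to 14% of operated Subjects were withdrawn yet received another THA, and nothing in the documents supports so many. This stands, and it limits the size of the point. It does not remove the gap, because section 8.2 itself provides for the case.

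The plan is also fairly transparent. Components used are recorded (8.2), withdrawals are tabulated by analysis set (11.10) and every reported event is listed by Subject (11.13). An implanted-only rate could be worked out from the data, but the planned table would not show it.

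Four stronger readings are tempting and are not supported:

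- **These Subjects have no follow-up.** Section 9.4 reads "Adverse events are reported from the time of surgery until the Subject's study participation has ended (i.e. completion of study or withdrawal of consent"; a surgeon's withdrawal for bone quality is neither of these. Whether events are still collected is unsettled. The dilution does not depend on the answer.
- **They cannot have any device-related event.** This is true of intraprosthetic dislocation. It is not certain otherwise, because the study article in section 4.3 also covers the cup, stem and head, and an event during an attempted implantation could be rated device-related. If it were, the table would mix populations: with x = 3, N = 30 and k = 1, it would read 4/31 = 12.9% against 10.0% among the implanted.
- **Confidence limits and the historical comparison of adverse events are distorted.** Section 11.13 plans numbers and percentages only. Section 11.12.4 compares primary, secondary and exploratory endpoints with DSJ_2018_02, not the general adverse event tables. The 1-year summary meant to support regulatory submissions (11.14) names only cup subsidence.
- **All safety percentages are wrong.** Keeping every operated Subject is defensible for SAEs, deaths, procedure-related events and intra-operative complications. Limiting those to the implanted would lose a death or SAE after a failed implantation attempt.

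**Conclusion.** The point holds in a limited form. Read literally, sections 6.3, 8.2, 11.5 and 11.13 put a Subject who is withdrawn intra-operatively but receives another THA into the denominator for device-related events. If such Subjects have no device-related event, the construct's percentage is lowered by k/(N+k).

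The size is conditional on k, which the documents do not give. At N = 30 it runs from nothing at k = 0, through 3.2% relative at k = 1, to 14.3% at k = 5. The low end is the more plausible, given the pre-operative screening. For intraprosthetic dislocation the defect is a missing denominator rather than a demonstrated bias. The primary RSA result and the other safety percentages are not called into question. The correction is worth making because the rule is ambiguous about exposure and the remedy needs no new data.

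**What to change.** Before the SAP is finalized:

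1. Keep the Safety Analysis Set (all operated Subjects) for SAEs, deaths, procedure-related events and intra-operative complications.
2. Add to section 11.5 an Implanted Set: enrolled Subjects implanted with the PINNACLE DM metal liner and the BI-MENTUM polyethylene liner. Name it in 11.13 as the denominator for device-related event percentages, and in 11.12.3 for the incidence of intraprosthetic dislocation.
3. List intra-operative withdrawals separately, with the reason, the components received and any events, including any device-related event during an attempted implantation, so that nothing is lost from view.
4. Reconcile section 8.2 with section 9.4 so that the protocol states whether adverse events are still collected after a surgeon-initiated withdrawal.

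The cost is a few sentences in the protocol and SAP, one extra denominator and one listing, from data already to be recorded. The downside for the sponsor is that device-related rates may read slightly less favourably. If no such withdrawal occurs, no Subject is added to the device-related denominator and the dilution is nil.
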